**Table 6. Outcome assessment areas in user survey**

Domain	Subdomain	Survey Topic
Experience with user aRMMs	User Guide / Reminder Card	
 
• Prior access to aRMM
 
• Mode of access to aRMM
 
• Perceived ease of access to aRMM
 
• Use of aRMM
 
• Perceived usefulness of aRMM
 
▪ Reasons for not using aRMM, if applicable
 

Knowledge	Comprehensive HIV-1 infection prevention strategies	
 
• Knowledge of susceptibility to HIV infection while on CAB-LA
 
• Measures to be taken to further reduce risk of HIV infection while on CAB-LA
 
• Knowledge of recommendation to consult with HCP when stopping CAB-LA
 

	Risk of developing drug resistance	
 
• Knowledge of whether CAB-LA can be used if infected with HIV or with unknown HIV infection status
 
• Knowledge of ways to reduce risk of getting HIV/developing resistance
 
• Knowledge that CAB-LA will remain in the body for up to one year from last injection
 

	Importance of CAB-LA adherence	
 
• Knowledge of CAB-LA dosing schedule including oral use (if applicable)
 
• Risks of not being adherent
 
• What to do in case of a missed injection
 

	Regular monitoring/HIV-1 seroconversion	
 
• Knowledge of HIV testing recommendations before and during CAB-LA use
 

Domain	Subdomain	Survey Topic
Behaviours	Comprehensive HIV-1 infection prevention strategies	
 
Discussions with HCPs regarding prevention strategies
 
Use of additional prevention strategies including condom use and, not needle sharing
 
Actions taken when stopping CAB-LA
 

	Risk of developing drug resistance	
 
Actions taken when stopping CAB-LA (among users who have stopped CAB-LA)
 

	Importance of CAB-LA adherence	
 
Frequency of attending planned appointments
 

The full list of variables for the user primary objective survey are available in Annex 2.

***Outcomes Assessment – Primary Objectives***

For the primary objectives:

- Access of aRMMs will be assessed as the percentage of HCPs and users who accessed and read or used the materials.
- Knowledge outcomes will be assessed to summarize the level of correct or appropriate responses for individual questions and for individual HCPs and CAB-LA users. The proportion of correct responses to individual questions will be assessed across HCPs and CAB-LA users, as well as the proportion of correct responses among individual HCPs and CAB-LA users across all knowledge questions.
- As there is only one question for the attitude domain (for HCPs only), the proportion of HCPs with desirable attitude will be reported.
- Behaviour outcomes will be assessed to summarize the level of desirable or appropriate responses for individual questions and for individual HCPs and CAB-LA users. Most behaviour questions have Likert scale response option, in recognition that behaviour is typically observed on a continuum. Therefore, the response options that are somewhat optimal (e.g., “I sometimes provide counseling”) will be reported separately from the most optimal behaviour. The proportion of optimal and somewhat optimal responses to individual questions will be assessed across HCPs and CAB-LA users, as well as the proportion of both optimal and somewhat optimal responses among individual HCPs and CAB-LA users to all questions under each relevant risk message category and across all behaviour questions.

The survey questions that will elicit knowledge, attitude or behaviours, by risk message category are presented in Table 7.

**Table 7. Survey questions categorization by risk message category**

Risk Message Topic	User Survey		HCP Survey		
	Knowledge	Behaviour	Knowledge	Attitude	Behaviour
Comprehensive prevention strategy	Q31, Q32, Q38	Q47, Q48, Q49	Q13		Q30, Q33
Risk of developing drug resistance	Q36, Q37, Q39, Q40	Q51	Q15, Q16, Q17, Q23, Q24		Q32, Q39, Q40
Adherence	Q33, Q35, Q41, Q44, Q45	Q46	Q18, Q19, Q20, Q21, Q22	Q25	Q26, Q29, Q34
Regular monitoring/ HIV-1 seroconversion	Q34		Q14		Q27, Q28, Q31, Q35, Q36, Q37, Q38

**Abbreviations:** HCP, Healthcare provider; HIV, Human immunodeficiency virus; Q, question.

*Assessment of success*

For the HCP and CAB-LA user surveys, the proportion of correct or appropriate responses to the access, knowledge, attitude (for HCP), and behaviour questions related to the primary objective will be summarized, across questions, categories (access, knowledge, attitude, behaviours) and participants.

For this study, a success threshold (i.e., optimal knowledge, attitude, and behaviour) of 80%, which is commonly used by convention, will be adopted at the individual level. In other words, an individual will be deemed to have met the success threshold if they answer  $\geq 80\%$  of questions within each KAB domain correctly or appropriately. Therefore, there will be a separate score for knowledge and behaviour. At the population level, we propose a success cut-off of 70% defined as at least 70% of HCPs and CAB-LA users meeting the success threshold (i.e., answer  $\geq 80\%$  of questions within the KAB domain correctly or appropriately) at the time of assessment.

While some published KAB studies have conducted surveys at two time points, we will be conducting a one-time assessment because we anticipate that 70% of HCPs and CAB-LA PrEP users surveyed would likely achieve the success threshold.

Additional justification for conducting a one-time assessment is based on several challenges associated in conducting a two-time point outcome assessments among HCPs and CAB-LA users, which include: 1) evolving PrEP prescribing practices may lead to an expansion in HCPs prescribing PrEP over three years, and this demographic change in the profile of prescribers would make KAB trend comparisons between 18 months and at a future time (e.g. 3 years) less meaningful; 2) competing therapies, public health priority changes, and updated guidelines could shift user preferences or prescribing patterns, impacting CAB-LA uptake and introducing confounding variables that could undermine the ability to assess trends in retention reliably; and 3) users may discontinue CAB-LA or switch providers between 18 months and a future time (e.g., three years), posing challenges in maintaining a consistent cohort for meaningful comparisons over extended periods and determining if knowledge is retained, increased, or decreased by users. By concentrating efforts on the 18-month survey, we will obtain valuable insights on the KAB levels among HCPs and CAB-LA for PrEP users within a stable context while avoiding confounding variables and practical challenges associated with a longitudinal two-time point timeline.

***Outcome Variables – Secondary objectives***

For the secondary objectives, the HCP survey will collect data on HCP decision-making processes, experience prescribing or managing CAB-LA and oral PrEP use among their users, use of CAB-LA oral lead-in and oral bridging, -management of PK tail among those discontinuing CAB-LA, and attitudes towards CAB-LA.

The CAB-LA user survey will collect data on users’ decision-making process related to the use of oral PrEP and CAB-LA and reasons for initiating, switching to, or staying on CAB-LA; experiences with CAB-LA, including satisfaction and acceptability of the regimen, PrEP-related preferences, any benefits or limitations of HCP visit schedule, and the emotional and daily life impacts of using CAB-LA, utilization patterns of CAB-LA, and experiences of judgement for using CAB-LA and other PrEP.

The survey questions associated with each objective are presented in Table 8.

**Table 8. Survey questions categorization by secondary objective**

Objective	User Survey	HCP Survey
Demographics and clinical characteristics	20 questions	13 questions

Objective	User Survey	HCP Survey
Decision-making for PrEP and CAB-LA	3 questions	4 questions
Experience and satisfaction using PrEP and CAB-LA	12 questions	17 questions
CAB-LA oral lead-in and bridging (HCPs)	NA	8 questions
Management of PK tail (HCPs)	NA	5 questions
Attitudes towards CAB-LA (HCPs)	NA	2 questions
Utilization patterns (includes oral lead-in and bridging, and discontinuation; users)	19 questions	NA

**Abbreviations:** CAB-LA, Long-acting injectable cabotegravir (Apretude®); HCP, Healthcare provider; PK, pharmacokinetic; PrEP, Pre-exposure prophylaxis

*HCP survey*

The following variables will be extracted from the HCP survey:

**Table 9. HCP survey topics categorized by secondary objective**

Objective	Survey Topic
Decision making process for use of oral PrEP and CAB-LA	
 
• Who is offered PrEP
 
• Factors influencing decision to offer oral PrEP and CAB-LA
 
• Prescribers’ insights into user preferences (prescribers only)
 
• Reason for not initiating CAB-LA
 

Experience prescribing and managing users on oral PrEP and CAB-LA, at the clinical level and among eligible individuals, including use of HIV testing	
 
• Factors influencing the number of CAB-LA users that clinics can manage
 
• Reasons for switching PrEP methods
 
• Identifying number of patients who could be potential CAB-LA users
 
• Barriers to implementation of CAB-LA
 
• Frequency of HIV and STI testing for patients on oral PrEP and CAB-LA
 
• Type of HIV testing
 
• Clinics’ ability to have non-prescribers administer oral PrEP;
 

Objective	Survey Topic
	
 
• Authorization of who can administer oral PrEP and Apretude
 
• Decision-making process for discontinuing CAB-LA (prescribers only)
 
• Proportion discontinued CAB-LA
 
• Measures taken in the first week on CAB-LA
 
• Reasons for discontinuing CAB-LA
 

Use of oral lead-in and oral bridging	
 
• Candidates for oral lead-in (prescribers only)
 
• Oral lead-in drug, frequency and duration
 
• Decision-making processes for oral lead-in (prescribers only)
 
• Oral bridging drug, frequency and duration
 
• Decision-making processes for oral bridging (prescribers only)
 
• Oral lead-in and bridging drugs prescribed
 

Management of pharmacokinetic tail among those who discontinue CAB-LA	
 
• User counseling regarding residual CAB-LA concentrations
 
• Timing of counseling
 
• Monitoring of patients after discontinuation
 
• Patients use of oral PrEP after discontinuing CAB-LA
 
• Duration of oral PrEP use after discontinuing CAB-LA, by sex
 

Attitudes towards CAB-LA	
 
• Opinions regarding administering and implementing CAB-LA
 
• Perceived benefits of implementing CAB-LA in practice
 

*User survey*

The following variables will be extracted from the user survey:

**Table 10.** User survey topics categorized by secondary objective

Objective	Survey Topics
Decision-making processes for use of oral PrEP and CAB-LA	
 
• Level of shared decision-making
 
• Prior treatment
 
• Reasons for initiating CAB-LA
 

Experience using oral and CAB-LA, including emotional and daily life impact and treatment satisfaction	
 
• Satisfaction with medication
 
• Drug administration preferences
 
• Limitations of CAB-LA
 
• PrEP preferences
 

#{vault:document\_date\_\_v}

Protocol for Non-Interventional Studies PASS Studies and Non-PASS Studies (4.0) March 2024

Template Doc ID: TMF-15706807

Parent Doc ID: VQD-SOP-066694

Objective	Survey Topics
	
 
• Satisfaction with injections over oral PrEP
 
• Worry of missing doses
 
• Judgement due to use of oral PrEP prior to CAB-LA                             
 
○ Frequency, occurrences, feelings associated
 
 
 
• Judgement due to use of CAB-LA                             
 
○ Frequency, occurrences, feelings associated
 
 
 
• CAB-LA impact on unfair judgement
 

Utilization patterns include adherence, oral lead-in, bridging and discontinuation
	
 
• Oral lead-in use and reasons for use
 
• Missed injections                             
 
○ Planned vs. unplanned, reasons for missing
 
 
 
• Use of and type of oral bridging
 
• Acceptability of oral bridging
 
• Current CAB-LA use status
 
• Reasons for continuing CAB-LA
 
• Reasons and decision-making processes for discontinuing CAB-LA
 
• Receipt of counselling for HIV testing after discontinuation
 
• Acceptability of HIV testing after discontinuation
 
• Using other PrEP after discontinuing CAB-LA
 
• Receipt of counselling to initiate another PrEP after discontinuing CAB-LA
 
• Acceptability of counselling to start another PrEP
 
• Future consideration of CAB-LA
 

*Apretude Support PSP*

The following variables will be extracted from the PSP database:

**Table 11. Variables extracted from the Apretude Supports Program database**

Apretude Supports Program database variables

 
• Patient ID
 

 
• Enrolment date
 

 
• Patient status
 

 
• Patient status date
 

 
• Appointment number
 

 
• Oral lead-in use
 

Apretude Supports Program database variables	
•	Initiation injection dosing schedule
•	2nd initiation injection dosing schedule
•	Days supplied
•	Injection type
•	First dose date
•	Initial injection dose
•	Current injection dose
•	Baseline target treatment date
•	Current target treatment date
•	Appointment dates 
 
○ Confirmed appointment, missed appointment, cancelled/rescheduled appointment, patient file appointment
 

•	Reason for missed injection
•	Oral bridging use 
 
○ Planned/unplanned oral bridging, oral bridging agent, dose, planned leave start and end dates
 

•	Returned appointment date or target treatment date
•	Re-initiation appointment date
•	Status date discontinued
•	Status reason discontinued 
 
○ Missed injection status
 

•	Incomplete reason

The following utilization pattern outcomes will be assessed based on the PSP data:

**Table 12. Outcome assessed for secondary objective #9**

Category	Sub-category	Details
Utilization patterns	• Use of oral lead-in	
 
▪ Frequency of use
 
▪ Duration of use
 

	• Use of oral bridging	
	• Adherence to CAB-LA	
 
▪ Measured as proportion of days covered (PDC)                             
 
○ Ratio of number of days the user is covered by the medication during a specific period to the total number of days within that period                                     
 
• Measured on user’s coverage (days supplied) with CAB-LA
 
 
 
 
 

Category	Sub-category	Details
		
 
Based on available follow-up time within the Apretude Supports Program database
 

	
 
Timing of injections (relative to labeled dosing schedule)
 
	
 
Early, on-time, late (with 7-day grace period)
 

	
 
Gaps in therapy
 
	
 
Missed injections (relative to labeled dosing schedule), reasons for missed injections
 
Missed injections being planned or unplanned
 
Use of oral bridging, planned or unplanned                             
 
Type and frequency of oral bridging agents used
 
Duration of oral bridging
 
 
 

	
 
Persistence on CAB-LA
 
	
 
Time to discontinuation
 
% of users who remain on drug, and are still at risk of HIV infection, at end of follow-up (will depend on data availability for at-risk status, either through PSP variables or through linkage with survey data)
 

	
 
Discontinuation
 
	
 
Rates of discontinuation
 
Reasons for discontinuation
 

### 7.3.3. Confounders and Effect Modifiers

None identified

### 7.4. Data Sources

#### Primary Objectives

This study will include data collection through surveying of HCPs and CAB-LA users. The HCP study population will comprise physicians, nurses, and pharmacists who prescribe

#{vault:document\_date\_\_v}

Protocol for Non-Interventional Studies PASS Studies and Non-PASS Studies (4.0) March 2024

Template Doc ID: TMF-15706807

Parent Doc ID: VQD-SOP-066694

CAB-LA or who manage CAB-LA use among CAB-LA users in Canada. HCPs will be recruited across different clinical settings representative of how care is offered in Canada, including but not limited to hospitals, outpatient clinics, and pharmacies across Canada. CAB-LA users will be recruited from different clinical settings where they access PrEP (for example, but not limited to hospitals, outpatient clinics, and pharmacies) across Canada.

## Secondary Objectives

For the secondary objectives, this study will include data collection through surveying of HCPs and CAB-LA users and a retrospective analysis of data from the Apretude Supports Program.

### Apretude Supports Program Database Analysis

The retrospective database analysis will utilize the Apretude Supports Program database run by a third-party vendor (Bayshore Healthcare), which is responsible for managing and administering the program, including capturing participant information in the Apretude Supports Program database. Enrolment forms for the Apretude Supports Program which are sent to Bayshore Healthcare include participants' informed consent to allow ViiV Healthcare and Bayshore Healthcare to collect, use and analyze Apretude Supports Program data for the purposes of research. The data collected by Bayshore may be collected in aggregate and anonymized form and used for research (per patient consent in the enrollment form). Data will be included for individuals initiating CAB-LA between July 2024 and October 2026, with an interim analysis taking place in Q1/Q2 2026 for data available up to that time point (July 2024 to Q1/Q2 2026). As this will be an analysis of already collected data (secondary data collection), variables and data will be dependent on the data collected with the Apretude Supports Program, as detailed in Annex 1.

**Table 13. Levels of precision calculated by target sample size and proportion of correct responses**

	Correct response rate (%)				
Sample size	50	60	70	80	90
50	+/-13.9	+/-13.6	+/-12.7	+/-11.1	+/-8.3
100	+/-9.8	+/-9.6	+/-9.0	+/-7.8	+/-5.9
250	+/-6.2	+/-6.1	+/-5.7	+/-5.0	+/-3.7
500	+/-4.4	+/-4.3	+/-4.0	+/-3.5	+/-2.6

For binary % outcomes, based on the maximum variation assumption (p=0.50), the expected 95% confidence interval precision is +/- 9.8% for a sample size of 100 and +/- 6.2% for a sample size of 250.

The target sample size for the HCP survey is n=100 HCPs; the target sample size for the CAB-LA user survey is n=250. Thus, with respect to the primary study objective as reported by users, the maximum width of the expected confidence interval is +/- 9.8% for HCPs and +/- 6.2% for users.

**Secondary Objectives**

*HCP and CAB-LA User Survey*

The HCP and CAB-LA user participants will complete one survey, addressing questions for both the primary and secondary objectives.

*Apretude Supports Program Database Analysis*

The sample for the Apretude Supports Program database analysis will include eligible CAB-LA users in the database at the time of the interim and final analyses. It is anticipated that at least 450 eligible CAB-LA users will be included at the time of final analysis.

## 7.5.2. Recruitment strategy

### Pilot testing

Pilot testing for the surveys will be conducted as the final stage of survey development (before REB submission) to identify and address potential issues that could affect data quality, including reducing incomplete responses, assessing clarity and understandability of questions, evaluating the appropriateness of language and terminology, estimating the time required to complete the survey, and ensuring that the structure and flow of the survey are logical and user-friendly. Five participants will be sought to pilot test the survey and provide feedback (five HCPs for the HCP survey, and five CAB-LA community members (i.e. AIDS support organization workers who provide support in the care of PrEP users) for the user survey). Each of these participants will participate in a one-on-one virtual session to review the survey with a study team member and provide feedback on the survey questions and response options. Feedback from these sessions will be reviewed by the research team and used to improve and implement any relevant changes to the survey. Once the feedback is compiled, the surveys will be updated as needed and general recruitment will commence as described below. The pilot testing will not collect any data to be analysed or included in the study database.

### Recruitment of HCPs

The recruitment strategy will target HCPs across different institutional and community settings representative of how care is offered in Canada, including but not limited to hospitals, outpatient clinics, pharmacies, community clinics, and private practices across Canada. Recruitment will be stratified by provider type. To adequately address objectives related to prescriber decision making, given that not all HCPs administering injections will be the ones making prescribing decisions, a minimum target of 50% prescribers has been set (i.e., recruitment for non-prescribing HCPs will be halted once the sample size reaches 50). HCP recruitment may take place through an established recruitment vendor for medical research (Medicys), with minimum targets for recruitment by prescriber status, clinical setting, and HCP type. Recruitment and survey materials for the secondary objectives will not contain language suggesting that the study was requested by HC.

**Table 14. Target sample sizes according to selected characteristics**

HCPs (total n = 100)	
Characteristic	Minimum n
Prescriber status	
Prescribes or can prescribe CAB-LA	50
Clinical setting	
Hospital	25
Outpatient clinic	25

\$(vault:document\_date\_\_v)

Protocol for Non-Interventional Studies PASS Studies and Non-PASS Studies (4.0) March 2024

Template Doc ID: TMF-15706807

Parent Doc ID: VQD-SOP-066694

HCPs (total n = 100)	
Pharmacy	25
HCP type	
Physician	15
Nurse	15
Pharmacist	15

**Abbreviations:** CAB-LA, Long-acting injectable cabotegravir (Apretude); HCP, Healthcare provider.

### Recruitment of CAB-LA Users

For the survey component of the study, CAB-LA users will be recruited using recruitment flyers/posters with a quick response (QR) code linked to the survey, displayed at different clinical settings where they access PrEP (for example, but not limited to hospitals, outpatient clinics, and pharmacies) across Canada. In addition, HCPs participating in the HCP survey may also direct CAB-LA users to the QR code for the survey. To reach target sample sizes and to ensure representativeness of the user sample, recruitment may additionally be conducted through Mediscys. Recruitment of CAB-LA users will be conducted in geographic regions where CAB-LA is publicly listed. As access expands across Canada, recruitment will also be expanded to ensure representation from all possible regions. The data will be analyzed by geographical location, with some regions anticipated to be grouped together based on available sample size (e.g., Western Canada). Recruitment and survey materials for the secondary objectives will not contain language suggesting that the study was requested by HC.

### Logistics and Monitoring

Individuals who are interested in participating will be directed to a brief screening questionnaire to assess eligibility for survey participation against study inclusion criteria. If the individual is identified as eligible to participate in the survey based on screener responses, they will be directed to an electronic version of the consent form. Once they have electronically indicated their consent to participate (selecting a consent statement and providing an electronic signature), they will subsequently be directed to complete the survey. Based on personal information collected during the screening and consent process, including participant name and email address, a check will be performed to ensure that there is no prior completion of the same survey in the system using the same name and email entered. The purpose of this check is to prevent participants from completing the same survey multiple times. To help optimize response rates, up to two reminder emails will be sent to individuals who have not completed the survey (one after 7 days and another after 14 days). To promote further education, correct responses to the survey questions, where applicable, will be displayed immediately after submission of the survey (before a participant has exited the survey) in a PDF file. A link to the aRMMs will be included in the PDF and on the online survey platform for future reference.

For each survey, a live dashboard will be set up to monitor recruitment progress against targets, allowing for adjustments to the recruitment strategy to be made in real time, as needed (e.g., increase the number of recruitment sites and/or target recruitment of certain participant groups to improve representativeness).

HCPs will receive a one-time payment of \$350 upon completing the survey, while CAB-LA users will receive \$100. For the pilot testing, each of the 5 HCPs will be compensated \$350, and each of the 5 community members will receive \$100. Remuneration details will be provided in the consent form. For both surveys, unique survey links will be generated for each participant. The unique link will enable participants to save their progress and return to complete the survey at a later time, minimizing potential incomplete responses. In addition, checks will be in place to ensure that each link can only be used once to complete the survey and receive payment. Checks may include a combination of the following: 1) checking IP addresses; 2) checking for duplicate email addresses for payment; 3) checking for suspicious email addresses; 4) running PercentMatch statistical function assess the level of identical observations in the survey dataset; 5) checking for realistic survey completion times. Recruitment will continue for approximately five months, unless the closing criterion is met. The closing criterion for the survey is reaching the maximum sample size of 100 HCPs and 250 CAB-LA users.

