#### *User KAB Survey*

To be eligible for participation in the study, individuals must meet all the following criteria:

- Provide a signed and dated informed consent form for participation in this research study;
  - Be capable of providing informed consent;
- Be at least 16 years of age at the time of consent into the study;
- Must be able to independently complete the survey in English or French; and
  - Have received at least one injection of CAB-LA for HIV PrEP.

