## 7.8. Quality Control and Quality Assurance

This study will be conducted according to local quality control processes. This procedure requires documented evidence that the study protocol has been correctly interpreted and executed.

This study will be conducted according to published best practices and guidance on the conduct of quantitative surveys, as well as Broadstreet Health Economics and Outcomes Research (HEOR) working practices to guide statistical analysis and validation. Details of these procedures are listed below, as are the details of a quality control (QC) independent review of final results to ensure that the study protocol has been correctly interpreted and executed.

Data will primarily be collected through securely hosted online surveys. CAB-LA users will have the option to complete a paper survey. The online surveys will be designed to not allow questions to be skipped (to avoid incomplete data); however, participants may select a “prefer not to answer” option, in particular for sensitive questions. Thus, incomplete questions are not expected for the online surveys; however, incomplete questions may occur for the paper survey. No imputation is planned for any missing data (incomplete questions or questions marked ‘prefer not to answer’). All data collected will be considered for the analysis, including for partially completed surveys. However, measures will be taken to optimize response rates (see section 7.5.2).

Additionally, the surveys will be designed to minimize the possibility of participants entering inappropriate responses. These design elements include using close-ended, true/false or multiple-choice options; allowing users to respond with “I’m not sure” or “Prefer not to answer” rather than participants entering erroneous responses; and restricting free text responses to only accept numeric data entries (where appropriate, e.g., entering participant age).

After the completion of the first surveys by HCPs and CAB-LA users, an analyst will assess response rate, as well as the quality of collected data. Data will be checked for missing, illogical, and inconsistent data, and automated data checks will also be conducted (e.g., range checking). Any implications regarding survey programming will be identified and

#{vault:document\_date\_\_v}

Protocol for Non-Interventional Studies PASS Studies and Non-PASS Studies (4.0) March 2024

Template Doc ID: TMF-15706807

Parent Doc ID: VQD-SOP-066694

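### The committed duplicate check for users needs name and email to match together, eligibility rests on screener answers, and no rule removes failed records from the primary 70% result

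*Protocol*

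**What the plan says.** Section 7.2.2 requires a survey user to "Have received at least one injection of CAB-LA for HIV PrEP". Under Recruitment of CAB-LA Users (Section 7.5.2), the main route is "recruitment flyers/posters with a quick response (QR) code linked to the survey", displayed in clinical settings. Providers in the HCP survey may also point users to the code, and a recruitment vendor may be used.

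Under Logistics and Monitoring (Section 7.5.2), interested people are "directed to a brief screening questionnaire to assess eligibility for survey participation against study inclusion criteria", and those who qualify on their screener responses go on to electronic consent. No clinic code, prescription or support-program record is said to confirm the injection. Section 7.1 mentions linkage to the support program only if feasible, and for a different purpose.

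Two controls on repeat entry are firm. One looks for "no prior completion of the same survey in the system using the same name and email entered". The other is a unique link that can be completed and paid once. Beyond these, "Checks may include a combination of the following": IP address, duplicate payment email, suspicious email, PercentMatch and completion time. No consequence for a record that fails is given there.

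Users are paid $100. The correct answers are shown as soon as the survey is submitted. Section 7.7 describes a sensitivity analysis, to be done if necessary, that leaves out respondents flagged for inconsistent answers or very short completion time.

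**The concern.** The user result is a percentage of respondents, judged against one cut-off: at least 70% must reach 80% within a domain (Section 7.3.2, Assessment of success). Every record that is not a distinct, eligible user enters numerator and denominator alike. Because recruitment closes at 250 users, each such record also takes a genuine user's place.

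Two kinds of invalid record are possible. A repeat taker can come back having seen the answers, which would tend to raise the knowledge percentage. A respondent who never received CAB-LA has had no reason to see the risk-minimization materials and would probably lower it. The survey is a one-time assessment for a regulatory commitment, and reassessment at 3 years is only a possibility (Section 7.10), so an error in either direction would not readily be corrected.

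**Working it through.** **1. What each control stops**

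- Name-and-email match: stops a person who re-enters both unchanged. As worded, a change of email alone defeats it.
- Single-use link: stops re-use of a link. It limits the link and not the person; someone who registers again as a new participant would receive a new link.
- IP, payment-email, suspicious-email, PercentMatch and completion-time checks: would catch some repeats if run. Their use and combination are optional. None shows that a single-entry respondent received an injection.
- Section 7.7 exclusion: triggered by inconsistency or speed, not by duplication or ineligibility, and applied only in a sensitivity analysis.

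**2. The plan's own precision**

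Half-width = 1.96 × √(p(1−p)/n), with n = 250 from Section 7.5.1.

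- p = 0.50: 1.96 × √(0.25/250) = 6.2 points, as stated.
- p = 0.70: 1.96 × √(0.21/250) = 5.7 points, as in Table 13.

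This covers sampling error only. Invalid records add bias that the interval does not show.

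**3. Illustration of the bias**

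Observed = (1−f)·p + f·q, where f is the share of invalid records, p the success rate in genuine users and q the success rate in invalid records. All three are assumptions; the protocol gives none of them. The cut-off is 0.70 × 250 = 175 users.

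- p = 0.75, q = 0.30: f = 10% gives 0.675 + 0.030 = 70.5%; f = 20% gives 0.600 + 0.060 = 66%. The cut-off is reached at f = (0.75−0.70)/(0.75−0.30) = 11.1%, about 28 of 250.
- p = 0.75, q = 0.95: f = 10% gives 77%; f = 20% gives 79%.

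Share needed to bring the expected figure to 70%, over a range:

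| Direction | p | q | f | Records of 250 |
|---|---|---|---|---|
| Down | 0.72 | 0.2 / 0.4 | 3.9% / 6.3% | 10 / 16 |
| Down | 0.75 | 0.2 / 0.4 | 9.1% / 14.3% | 23 / 36 |
| Down | 0.80 | 0.2 / 0.4 | 16.7% / 25% | 42 / 63 |
| Up | 0.68 | 1.0 / 0.9 | 6.3% / 9.1% | 16 / 23 |
| Up | 0.65 | 1.0 / 0.9 | 14.3% / 20% | 36 / 50 |
| Up | 0.60 | 1.0 / 0.9 | 25% / 33.3% | 63 / 84 |

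**4. Effect on the verdict**

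Probability that at least 175 of 250 succeed (sum of two binomials, exact), with 25 invalid records against none:

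- p = 0.75, q = 0.2: falls from 0.969 to 0.460.
- p = 0.65, q = 1.0: rises from 0.055 to 0.327.

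**The case against.** The other side has substance. Some stronger readings are tempting but are not supported:

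- **That the survey is open to anyone through a public poster.** The posters hang in clinical settings where PrEP is accessed, and a paper version may be completed at study sites as needed (Section 7.6). A code can be shared, but the protocol does not describe open public recruitment.
- **That name and email is the only firm check.** Single-use links are also a commitment. They do not identify the person, but they are a control.
- **That Section 7.8 keeps invalid records.** The sentence "All data collected will be considered for the analysis, including for partially completed surveys" follows the text on incomplete questions and no imputation. It is a missing-data rule. Section 7.8 also commits to checks for illogical and inconsistent data, with database changes documented.
- **That the screener gives away the qualifying answer.** It is not shown, and Annex 2 contains only file names, so its masking is unknown.
- **That the bias is known to overturn the result.** The values of f, p and q have no source in the protocol. Knowledge and behaviour are scored separately, and the answer-key route bears mainly on knowledge.

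Two further points are fair. Self-reported eligibility is a reasonable trade-off where participants may fear disclosure, and a statistical analysis plan may hold cleaning rules. Neither settles the matter. The screener, duplicate key and link rules are data-collection procedures that the protocol itself fixes, and later analysis cannot recover information never collected. The protocol also takes its own position on exclusion in Section 7.7, and that position does not cover duplicates or ineligible respondents.

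**Conclusion.** The point holds as a weakness in a stated rule. Eligibility rests on screener responses with no stated confirmation of an injection. The committed person-level check misses a repeat under a second email. The checks that might catch it are discretionary and have no stated consequence for the primary analysis. This rests on reading the duplicate check as requiring both fields to match, which is its plain sense.

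The size and direction of the bias cannot be derived from the document. The 11% figure depends on assumed success of 75% in genuine users and 30% in invalid records; other assumptions move the threshold widely or reverse the direction. The visible limitations text (Section 7.9, partly redacted) covers selection, reporting and recall bias and looking up answers, but not false eligibility or duplicate entry. The change is worth making because it is cheap and the verdict turns on a single cut-off.

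**What to change.** - **Logistics and Monitoring, duplicate check:** treat a match on name OR email OR payment email as a possible duplicate. Resolve it blind to KAB scores and keep only the first completion. Do this while identifiers are still held, since Section 8.2 keeps study IDs unlinked from them.
- **Logistics and Monitoring, listed checks:** make them mandatory for every record.
- **Section 7.7:** state that confirmed duplicates and records failing eligibility are removed from the primary analysis, with counts by reason, and make the all-records analysis the sensitivity analysis.
- **Screener, if it does not already do so:** ask which PrEP product was received from a list, with month of first injection and province or site type. The qualifying answer is then not revealed and no scored content is used.
- **Section 7.9:** say that eligibility remains self-declared. A masked screener reduces false eligibility but does not verify receipt of an injection.

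The cost is a few screener items and a written cleaning rule, with no new data source and no change in sample size. The downside is that a few genuine users may be queried or lost.
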